8.1 Clinical Assessments

8.1.1 Concomitant Medications

All concomitant medication and concurrent therapies will be documented at baseline and post-intervention, and at early termination when applicable. Dose, route, unit frequency of administration, and indication for administration and dates of medication will be captured.

8.1.2 Demographics

Demographic information (will be recorded at Visit 1 (Consent and baseline):

- date of birth
- sex
- race
- address
- email
- phone number

8.2 Medical History

Relevant medical history, including history of current disease will be recorded at Visit 1 (Consent and baseline).

8.3 Clinical Assessments

- CGM metrics including time >120 and GV
 - CGM will be fully blinded to the participant, unless on GEM so they may assess lifestyle modifications, and used to collect baseline and primary outcome data in a manner that will not bias RC subjects' activity as the CGM is programmed not to display values, only record values
- Height/Weight and BMI
- Blood pressure
- A1C
- Total cholesterol
- Triglycerides
- HDL
- LDL
- Presence of Atrial fibrillation
- Comprehensive proteomics

8.4 Psychological Assessments

- Health Questionnaires (PHQ-8)-measures depression
- Modified Diabetes Knowledge Scale
- Modified Diabetes Empowerment Scale
- Modified Treatment optimization scale
- Motivation and Attitudes Toward Changing Health Scale (MATCH)

8.5 Behavioral Assessments

- Carbohydrate Routine Consumption Scale
- Activity monitor that measures sedentary behavior, total steps and minutes of moderate to vigorous physical activity

8.6 Other Assessments

- Program Importance Questionnaire

8.7 Adverse Events

Information regarding occurrence of adverse events will be captured throughout the study. Duration (start and stop dates), severity/grade, outcome, treatment and relation to intervention will be recorded on the case report form (CRF).

9 EVALUATIONS BY VISIT

There will be a baseline assessment, then a 1-month treatment period, followed by a 4.5-month post assessment (see Figure).

9.1 Prescreening and PCP Approval

1. Prescreen via phone call
2. If eligible after phone call, send HIPAA-A form
3. Once HIPAA-A is returned to study team, send letter to PCP regarding approval for participation
4. Once PCP approval is received, call participant to schedule Visit 1

9.2 Visit 1: Consent and Baseline (all subjects)

1. Obtain written informed consent
2. Record appropriate demographics, medical history, and concomitant medications
3. Perform clinical assessments
4. Collect fingerstick A1c using DCA Vantage A1c machine to confirm eligibility. If participant is ineligible they will be informed and asked if they would like to be contacted for future prediabetes or diabetes studies. If

yes, they will be offered the Opportunity to join the Primary Care Diabetes Lab patient registry. If patient is eligible, then:

- a. Collect blood for clinical laboratory tests, including A1c and proteomics
 - b. Place blinded CGM and blinded activity monitor
 - c. Configure participant activity monitor app for blinded data capture and connect to study team account
 - d. Perform psychological assessments
 - e. Perform behavioral assessments
 - f. Randomization (results blinded to participant) after the above steps completed
 - g. Schedule GEM Start visit (for participants randomized to intervention).
 - h. Schedule RC start (for participants randomized to RC)
5. If the DCA Vantage A1c machine is not available or participant prefers venipuncture then blood will be collected for clinical laboratory tests, including proteomics and eligibility will be confirmed with A1c results prior to steps b-h above

If eligible, Visit 2 will be scheduled via phone call. If ineligible, participant will be informed and will be asked if they would like to be contacted for future prediabetes or diabetes studies. If yes, they will be offered the opportunity to join the Primary Care Diabetes Lab patient registry.

We will reach out to participants who are ineligible some time after their initial screening visit to see if they would like to come back in for a re-screen to repeat labs and/or the POC A1c test to see if they now qualify. All other procedures will remain the same.

9.3 Visit 2- Secondary Baseline (All subjects who are not able to confirm eligibility at Visit 1 will return for this Visit. If eligibility confirmed at Visit 1 then these steps are completed at that time.)

1. Place blinded CGM and blinded activity monitor
2. Configure participant activity monitor app for blinded data capture and connect to study team account
3. Randomization (result blinded to participant)
4. Perform psychological assessments
5. Perform behavioral assessments
6. Randomization (result blinded to participant). Randomization will not occur until steps 1-5 have been completed.
7. Schedule GEM Start visit (for participants randomized to intervention)
8. Schedule RC Start visit (for participants randomized to RC)

9.4 Visit 2/3– Start

9.4.1 RC Start (for participants randomized to RC), at least and as close as practical to 14 days following Secondary Baseline visit

1. History review, assess for AEs since last visit
2. Notify participant of randomization to RC
3. Blinded CGM data acquisition
4. Collect activity monitor
5. Schedule Follow Up visit for 4.5 months later (+/-2 weeks)
6. Schedule reminder contact for 2 weeks before next Visit; during contact, ask about interest in GEM if eligible

9.4.2 GEM Start (GEM subjects only)

1. History review, assess for AEs since last visit
2. Notify participant of randomization to GEM
3. Blinded CGM data acquisition
4. Instruct participant on unblinded Freestyle Libre 2 CGM
 - a. Instruct on placement, use, strongly encourage scanning 20-40 times a day, but at a minimum scanning at least every 8 hours
 - b. Establish participant account
 - c. Connect to study account
5. Instruct participant on activity monitor
 - a. Instruct on use
 - b. Reconfigure smartphone settings to unblind activity date
 - c. Verify participant account connection to study account
6. Review the GEM manual and read Unit 1 to ensure the participant understands the program. Encourage to complete 4 daily diary logs. Encourage significant other (if applicable) to also be present. Document whether significant other is present. To accommodate individual learning styles this may be done anytime within 1 week of the GEM Start Visit.
7. Set up text messaging (content, timing, frequency)
8. Schedule follow-up contact 2 weeks and 6 weeks later (when probability of dropout from lifestyle intervention peaks). Assess satisfaction with text messaging and change content/timing/frequency if necessary (and document).
9. Schedule Follow-up Visit for 4.5 months later (+/-2 weeks)
10. Schedule reminder contact for 2 weeks before next Visit; at that time, contact participant to assure they have a Libre 2 sensor inserted to collect the 14 days of end of study data.

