Description of Study Intervention	Blinded CGM data (obtained through the use of the Libre Pro) and blinded activity data (obtained through the use of a FitBit) will be obtained for 2 weeks on all participants at the start and end of the study, and baseline clinical data collection and psychosocial scales will be completed prior to randomization. The intervention group will be given Libre 2 supplies for 4 months, an activity monitor, and the 4-chapter GEM paper guide. The intervention group will complete a virtual or inperson study visit where they will receive instructions on how to apply their unblinded Freestyle Libre and connect it to the study account, as well as how to

	
register their Fitbit to the study account. If the visit will be conducted remotely, participants will be mailed their CGM, Fitbit, and the GEM manual. Participants will receive one telephone call to review use of the GEM Guide and call at two weeks and six weeks later when the probability of dropouts from lifestyle intervention peaks. Participants will follow the self-directed GEM guide for 4 months (a 1-month treatment period followed by a 3-month maintenance period) while wearing a FitBit activity monitor and a Freestyle Libre 2 CGM. Participants will be given this guide and a study email so they can easily ask questions about the GEM program during treatment. Fielding GEM questions will help the study progress smoothly and will gain information that might improve the Guide in the future. Relevant questions and corresponding answers will be posted on a study website for all participants to review, if desired. However, all medical management questions will be referred back to the participant's treating physician. The GEM Guide for Prediabetes contains the following information in four chapters: Glucose Impact of Routine Choices, Recovering from BG Excursions, Reducing BG Excursions, and Maintenance. The RC group will follow recommendations from their primary care physicians and clinicians that will be tracked for later analysis. RC participants will have the opportunity to receive the intervention four months after consenting and completing of the RC pre-post assessments. Comprehensive proteomics analysis will be done at the same time after all samples have been collected.

Study Duration	
This study will last approximately 24 months from the beginning of subject recruitment to data analysis.

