5.2.2 Primary Endpoint

- pre-post reduction in percentage of CGM readings >120, from blinded pre-post LibrePro.

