9.5 Visit 3/4 – Study Period 1 End

9.5.1 RC End (All subjects)

1. History review, assess for AEs since last visit
2. Give participant blinded CGM sensor and activity monitor and instruction for returning devices via mail if not doing GEM.
3. Perform clinical assessments
4. Perform psychological assessments
5. Perform behavioral assessments
6. Collect blood for clinical laboratory tests, including proteomics
7. Assess interest/appropriateness of crossing over to GEM
 - a. If crossing over to GEM, proceed to schedule visit 5 once A1c is confirmed via phone call.
 - b. If not crossing over to GEM, participation complete once CGMs returned via mail.

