9.5.2 GEM End (Study Period 1 End)

1. History review, assess for AEs since last visit
2. Perform clinical assessments
3. Download CGM data
4. Perform clinical assessments
5. Perform psychological assessments

6. Perform behavioral assessments
7. Complete Program Importance Scale
8. Collect blood for clinical laboratory tests, including proteomics
9. Place blinded CGM and activity monitor and instruct on how to mail back blinded CGM.

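### The protocol contradicts itself on which CGM supplies the GEM arm's post value for the primary endpoint: blinded Libre Pro after the end visit, or unblinded Libre 2 before it

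*Combined protocol and SAP*

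**What the plan says.** **Text that names one source.** Section 5.2.2 defines the primary endpoint as "pre-post reduction in percentage of CGM readings >120, from blinded pre-post LibrePro". The Protocol Summary and Section 4.1 agree. The intervention description in the Protocol Summary identifies the blinded device, "Blinded CGM data (obtained through the use of the Libre Pro", and says two weeks of such data are taken on every participant at both ends of the study. At the period 1 end visit the GEM step is "Place blinded CGM and activity monitor and instruct on how to mail back blinded CGM" (9.5.2). The RC step is "Give participant blinded CGM sensor and activity monitor and instruction for returning devices via mail if not doing GEM" (9.5.1). Appendix 1 marks blinded placement under both GEM End and RC End.

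**Text that points elsewhere, for GEM only.** At the reminder two weeks before the end visit, staff are to "contact participant to assure they have a Libre 2 sensor inserted to collect the 14 days of end of study data" (9.4.2 step 10, repeated in 9.6 step 9). At the end visit, before the blinded sensor goes on, the step is "Download CGM data" (9.5.2 step 3; also in 9.7.1). Section 8.3 describes the CGM as blinded "unless on GEM so they may assess lifestyle modifications, and used to collect baseline and primary outcome data". The matching RC reminder is only "Schedule reminder contact for 2 weeks before next Visit; during contact, ask about interest in GEM if eligible" (9.4.1) and asks for no sensor.

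**The analysis section.** Sections 11 and 11.3 give the tests (ANCOVA on change, t-tests, paired t-tests in period 2). They name no device, window, or order of precedence between sources.

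**The concern.** GEM has two 14-day records that could be called the post value. One comes from the Libre 2, which the participant can read, and ends at the final visit. The other comes from the blinded sensor and begins at that visit. RC has only the second. Both arms have a blinded Libre Pro baseline.

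If the Libre 2 record were used for GEM, the between-arm contrast would mix the effect of GEM with three other differences: the device, live glucose feedback during measurement, and the calendar window. Each would be present in one arm and absent in the other. Within the GEM arm, the pre-post change would also run from one device to another.

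The likeliest route is missing data. The blinded sensor is worn after the last visit and returned by mail, so some loss is foreseeable. Section 11.1 puts all randomized subjects in the analysis, but no missing-data rule is given. For a GEM participant whose sensor never arrives, the downloaded Libre 2 data would be at hand; for an RC participant there is nothing equivalent.

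The trial is meant to supply an effect size for a follow-up application (Section 5.1), so an error here would carry into the next trial's sample size.

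**Working it through.** The plan states no power, SD, effect size or device difference, so it has no figure on this point to reproduce. The check is a comparison of the text, then the algebra of the bias, then an illustration.

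**1. Sources of the post value, by arm**

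| | Before end visit | After end visit |
|---|---|---|
| GEM, period 1 | Libre 2, unblinded, 14 days (9.4.2 step 10), downloaded at visit (9.5.2 step 3) | Blinded sensor (9.5.2 step 9) |
| RC, period 1 | None (9.4.1) | Blinded sensor (9.5.1 step 2) |
| Crossover GEM, period 2 | Libre 2, unblinded, 14 days (9.6 step 9), downloaded at visit (9.7.1) | Blinded sensor (9.7.1) |

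The endpoint definition selects the right-hand column. Section 8.3, read literally, and 9.4.2 and 9.6 allow the left-hand column for GEM. No section excludes Libre 2 data from the primary endpoint. The period 2 paired test has the same ambiguity: its baseline is the blinded wear given at RC End, while its post value has two candidates.

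**2. Why adjustment does not help**

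Let δ be the combined shift in % readings above 120 from device, feedback and window when Libre 2 replaces Libre Pro.

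- GEM change = (post + δ) − Libre Pro baseline
- RC change = post − Libre Pro baseline
- Expected difference = treatment effect + δ

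δ is carried by the arm indicator and by nothing measured at baseline, so the ANCOVA group coefficient contains it in full. If Libre 2 is substituted for only a fraction p of GEM participants, and δ is constant, the bias is p × δ. With Libre Pro in both arms, p = 0 and this bias is zero.

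**3. Illustration: sensitivity of the metric (assumed offsets)**

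The only documented input is the 13% of readings above 120 in non-diabetic adults (Section 4.1). Normality, the SDs, the mean of 115 and the 5 mg/dL offset are assumptions.

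- SD 17: mean = 120 − 1.126 × 17 = 100.9 mg/dL. An offset of +5 gives 20.3%; −5 gives 7.8%.
- Mean 115, SD 22: 41.0% above 120. An offset of +5 gives 50.0%; −5 gives 32.5%.

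So an offset of 5 mg/dL, if there were one, would move the endpoint by about 5 to 9 percentage points.

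**4. Illustration: false positives**

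Assumptions: no true effect, two-sided alpha 0.05, 30 completers, and offset b in SDs of the change score applied to every GEM post value. Two-sample t-test with df = n1 + n2 − 2 = 28 and noncentrality b/√(1/n1 + 1/n2).

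| b | 15 v 15 | 20 v 10 |
|---|---|---|
| 0 | 5.0% | 5.0% |
| 0.10 | 5.8% | 5.7% |
| 0.25 | 10.1% | 9.6% |
| 0.50 | 26.2% | 23.9% |
| 0.75 | 50.9% | 46.4% |

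For example, at b = 0.50 and 15 v 15 the noncentrality is 0.50/0.365 = 1.37.

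**The case against.** The strongest reply is that the source is already fixed. The endpoint is tied to blinded Libre Pro in the Protocol Summary, Section 4.1 and Section 5.2.2, and the visit steps and Appendix 1 place a blinded sensor in both arms. A Libre 2 reading does not meet that definition. The 9.4.2 instruction sits in a visit checklist, Libre 2 wear is part of the intervention, and downloading it fits a process or adherence measure. The Section 8.3 exception can be read as distinguishing the intervention sensor from the outcome sensor.

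Most of this stands. A reader might infer that the plan schedules a device mismatch between arms, or leaves the analyst free to pick the more favourable source. The documents do not support either inference: no passage plans to analyse Libre 2 for GEM against Libre Pro for RC, and a switch would depart visibly from the stated endpoint.

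Two things remain. Section 8.3 puts the GEM exception in the very sentence about primary outcome data, and 9.4.2 and 9.6 give the Libre 2 wear a data-collection purpose at study end. Nothing in Section 11 settles the conflict or says what happens when a Libre Pro sensor is not returned.

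**Conclusion.** This is an unresolved contradiction about the source of the primary endpoint, and it should be settled before analysis. The bias is conditional: it arises only if Libre 2 data serve as the GEM post value or replace missing Libre Pro values. It would then be fully aligned with arm (δ, or p × δ for partial substitution) and beyond the reach of baseline adjustment. Its size and direction are unknown.

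A reader might take the 5 to 9 percentage points, or the 10.1% and 26.2% false-positive rates, as the expected error in this trial. The documents do not support that. They report no difference between Libre 2 and Libre Pro and give no SD. The figures show only that a threshold measure and a sample of about 30 are sensitive to an offset, should one exist.

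**What to change.** - In 5.2.2, 8.3 and 11.3, state that the post value in both arms, and for crossovers in period 2, comes only from the blinded Libre Pro placed at that period's end visit, over the same 14-day window relative to the visit.
- Reword 8.3 so that the GEM exception covers the intervention sensor and not outcome data. Reword 9.4.2 step 10 and 9.6 step 9 so that the Libre 2 wear is no longer described as the end-of-study record.
- Label the last 14 days of Libre 2 as supportive, on-intervention data.
- State that Libre 2 data are never substituted for a missing Libre Pro value.
- Reconcile the length of Libre 2 supply, which is 4 months in the Protocol Summary and 4.5 months in Section 5.1, since it bears on whether those supportive data exist.

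The cost is protocol and SAP wording, because both sensors are already scheduled. The downside is that GEM participants with only Libre 2 post data count as missing for the primary endpoint.

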9.5 Visit 3/4 – Study Period 1 End

9.5.1 RC End (All subjects)

1. History review, assess for AEs since last visit
2. Give participant blinded CGM sensor and activity monitor and instruction for returning devices via mail if not doing GEM.
3. Perform clinical assessments
4. Perform psychological assessments
5. Perform behavioral assessments
6. Collect blood for clinical laboratory tests, including proteomics
7. Assess interest/appropriateness of crossing over to GEM
 - a. If crossing over to GEM, proceed to schedule visit 5 once A1c is confirmed via phone call.
 - b. If not crossing over to GEM, participation complete once CGMs returned via mail.

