9.6 Visit 4/5- Study Period 2 Start

1. History review, assess for AEs since last visit
2. Blinded CGM data acquisition
3. Instruct participant on unblinded Freestyle Libre 2 CGM
 - a. Instruct on placement, use, strongly encourage scanning 20-40 times a day, but at a minimum scanning at least every 8 hours
 - b. Ensure participant account is working
 - c. Connect to study account
4. Instruct participant on activity monitor
 - a. Instruct on use
 - b. Reconfigure smartphone settings to unblind activity date
 - c. Verify participant account connection to study account
5. Review the GEM manual and read Unit 1 to ensure the participant understands the program. Encourage to complete 4 daily diary logs. Encourage significant other (if applicable) to also be present. Document whether significant other is present. To accommodate individual learning styles this may be done anytime within 1 week of the GEM Start Visit.
6. Set up text messaging (content, timing, frequency)
7. Schedule follow-up contact 2 weeks and 6 weeks later (when probability of dropout from lifestyle intervention peaks). Assess satisfaction with text messaging and change content/timing/frequency if necessary (and document).
8. Schedule Follow-up Visit for 4.5 months later (+/-2 weeks)
9. Schedule reminder contact for 2 weeks before next Visit; at that time, contact participant to assure they have a Libre 2 sensor inserted to collect the 14 days of end of study data.
10. Optional: For any participant coming off of the intervention, they will be asked at the end of the study visit 4 or 6, or contacted by email, phone, and/or letter to discuss if they would like to complete a short, semi-structured interview via audio and/or audio and video to provide feedback on the intervention to assist in improvements with the program for future studies. The interviews will be recorded and participants will be made aware of this. If any PHI is mentioned during the interview, it will be removed during the transcription process. This part is not required as part of the intervention and will not affect compensation or any study procedures.

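### The routine care arm's 14-day blinded post window opens only after participants have been asked about crossing over to GEM, so the control value of the primary endpoint may carry an anticipation effect that the GEM arm cannot have

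*Combined protocol and SAP*

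**What the plan says.** The primary endpoint (section 5.2.2) is the "pre-post reduction in percentage of CGM readings >120, from blinded pre-post LibrePro". The protocol summary says that these blinded data "will be obtained for 2 weeks on all participants at the start and end of the study".

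For the RC arm the relevant steps run as follows.

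- RC Start, 9.4.1 step 6: "Schedule reminder contact for 2 weeks before next Visit; during contact, ask about interest in GEM if eligible".
- RC End, 9.5.1 step 2: "Give participant blinded CGM sensor and activity monitor and instruction for returning devices via mail if not doing GEM".
- RC End, 9.5.1 step 7: "Assess interest/appropriateness of crossing over to GEM". Step 7a adds: "If crossing over to GEM, proceed to schedule visit 5 once A1c is confirmed via phone call". Step 7b, for those not crossing over, mentions no call.
- Appendix 1 sets the crossover GEM start (Visit 4/5) at 14 +/- 2 days.
- At that visit (9.6), step 2 is "Blinded CGM data acquisition". Instruction on the unblinded sensor, the manual and the text messages comes in later steps.

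The GEM arm's blinded post sensor is also placed at its end visit (9.5.2, step 9), with no crossover question. At baseline, sections 9.2 and 9.3 withhold the randomization result from the participant, who learns it at the Start visit about 14 days later (9.4.1 and 9.4.2, step 2).

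Section 11.3 compares the groups in period 1 with t-tests, and uses paired t-tests in the crossover group for period 2.

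**The concern.** Food intake and physical activity drive the endpoint, and the participant controls both. Someone who has just been asked about a low-carbohydrate and activity programme, and who may soon hear whether they qualify, could relax beforehand or could start changing early. Either would alter the 14 days that supply the RC post value.

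The protocol guards the baseline window against this by keeping allocation hidden until the sensor period is over. The RC post window has no matching protection. No passage asks RC participants to keep to their routine until the sensor comes off, or places the crossover discussion after it.

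The prompt exists in one arm only, so any shift it causes goes straight into the randomised comparison. Because the window is shared, the same shift also enters the period 2 paired comparison. Section 5.1 intends this pilot to supply the effect size for powering a follow-up application, so a distorted estimate would be carried forward.

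**Working it through.** The plan states no figure for this point, so there is none to reproduce. The check is a reconstruction of the timeline, followed by an illustration on assumed values.

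**Timeline, with RC End as day 0**

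| Event | Day | Source |
|---|---|---|
| First question about GEM | about -14 | 9.4.1 step 6 |
| Blinded post sensor handed over | 0 | 9.5.1 step 2; Appendix 1 |
| Second question about GEM | 0 | 9.5.1 step 7 |
| A1c confirmed, visit 5 scheduled (crossers only) | not stated; after day 0, before Visit 4/5 | 9.5.1 step 7a |
| Blinded post window | 0 to 14 | protocol summary |
| Crossover GEM start | 14 - 2 = 12 to 14 + 2 = 16 | Appendix 1 |

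**Share of the window exposed**

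- After the first GEM question: 14/14 = 100%.
- After a contact on day x: (14 - x)/14. Day 1 gives 13/14 = 93%; day 3 gives 11/14 = 79%; day 7 gives 7/14 = 50%; day 14 gives 0%.

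So the whole window follows the question, but the part that follows the A1c contact is unknown and could be nil.

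**Effect on the two analyses**

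Let f be the share of RC participants who change behaviour and s their change in percentage points of readings above 120. Neither is in the documents.

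- Shift in the RC post mean = f x exposed share x s.
- Anticipation over the whole window (exposed share = 1), f = 0.25 to 1.0 and s = 1 to 5: from 0.25 x 1 = 0.25 to 1.0 x 5 = 5 points. At f = 0.5: 0.5 to 2.5 points.
- A1c contact alone, f = 0.5: from 0.5 x 0.50 x 1 = 0.25 (day 7, s = 1) to 0.5 x 0.93 x 5 = 2.3 points (day 1, s = 5).

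For scale, section 4.1 puts non-diabetic adults at 13% of readings above 120.

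For period 2, Appendix 1 places no further blinded sensor between RC End and the start of crossover GEM, so the RC post window is the baseline. The paired mean moves by the share of crossers who shift, times s.

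**Direction.** If RC post readings rise, the RC reduction shrinks and the GEM advantage in period 1 grows; the period 2 baseline rises too, so the paired reduction also grows. If RC post readings fall, both estimates shrink. A shift shared by crossers and the RC arm as a whole therefore pushes both analyses the same way, but its sign is unknown.

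**The case against.** Several points on the other side are sound.

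- **No GEM content reaches RC participants inside the window.** A reader might infer that they are asked to start GEM, or that the window no longer reflects routine care. The text supports neither. They are asked about interest, and at Visit 4/5 the blinded data are acquired before the unblinded sensor, manual or messages are introduced.
- **The phone call is easily over-read.** It is written for crossers only, on no stated day, and the wording may describe how visit 5 is scheduled rather than how an A1c result is given. Section 5.1 reports that half of RC participants had an A1c outside the crossover range. It does not say that they were told so, or when.
- **Section 8.3 is not contradicted.** It says the blinded sensor is "used to collect baseline and primary outcome data in a manner that will not bias RC subjects' activity", but the sentence goes on to explain that values are not displayed. That protection is intact; the section makes no promise about crossover discussions.
- **Anticipation is built in.** The GEM offer is part of the design in the protocol summary and section 5.1, and RC participants know their allocation from RC Start. Moving a question removes a prompt, not the expectation.
- **Size is assumed.** Nothing links the planned 50% crossover share to the share who change behaviour, and relaxing and starting early could partly cancel.

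These points limit the claim to a possible effect. They do not alter the order of events, the one-arm exposure, or the double use of the window.

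**Conclusion.** The order of procedures is clear from the documents. The RC post window opens after participants have been asked about GEM, would-be crossers may also have the eligibility contact within it, and the GEM arm has neither. The RC post value of the primary endpoint, and with it the period 2 baseline, may therefore be affected by anticipation or feedback.

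The documents do not show that such an effect occurs, and they give neither its size nor its sign. The 0.5 to 2.5 points at f = 0.5 (0.25 to 5 over the wider range) rest wholly on assumed values and should be read as a scale, not an estimate. This is a worthwhile and inexpensive improvement to a pilot whose estimate is meant to inform a larger study; it is not a demonstrated bias.

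**What to change.** 1. In 9.4.1 step 6, keep the reminder contact and delete the question about interest in GEM.
2. Move 9.5.1 step 7, including the contact that confirms crossover eligibility and schedules visit 5, to after day 14 of the RC post sensor.
3. Give every RC participant the same device-return instructions whatever their crossover status. The GEM arm already mails its blinded sensor back (9.5.2 step 9).
4. Widen the 14 +/- 2 day window for Visit 4/5 in Appendix 1 accordingly. As written it also allows a visit on day 12, before 14 days have been recorded.
5. Communicate any A1c result needed for care in the same way in both arms. Record the dates of the question, any call and sensor wear.
6. For participants already measured, describe RC readings before and after the call, and crossers against non-crossers, as a sensitivity analysis. The second comparison is not randomised and should be labelled descriptive.
7. Reconcile 9.4.2 step 10, which describes 14 days of end-of-study data from a Libre 2 sensor worn before the GEM end visit, with 9.5.2 step 9, which places the blinded sensor at that visit, so that the timing and source of the GEM arm's post window are unambiguous.

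The cost is revised wording, one moved contact and a simpler return instruction. The downside is that crossover GEM starts some days later, leaving a short gap between the period 2 baseline and the start of the intervention.
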